## 8 STUDY ASSESSMENTS AND PROCEDURES

### 8.1 EFFICACY ASSESSMENTS

#### 8.1.1 SCREENING VISIT

Potential candidates for the study are evaluated by the Investigator or their designee as described below:

- The investigator or their designee must approve the candidate to be enrolled by verifying that the subject meets all of the inclusion criteria and none of the exclusion criteria, and that informed consent has been obtained from the patient. As part of the consenting process, the subject will be instructed on the scope of the study, potential risks and activities required to participate in the study, following a signed Informed Consent Form (ICF).
- If the subject meets the specified criteria and signs the ICF, they will be eligible to participate in the study for a period of 60 days. Over this period, the subject may return to the clinic upon onset of a migraine for an "on-demand appointment." The subject will receive the treatment, which will last up to 15 minutes, and will be followed for a period of 24 hours after the treatment, as specified herein.

- A subject may re-consent after the initial 60-day period if they did not receive a study intervention during that time period, if they continue to meet all inclusion/exclusion criteria. See **Section 5.3 Screen Failures** for more information.

---

### 8.1.2 BASELINE/TREATMENT VISIT

Upon arrival to the headache clinic during the acute onset period of a migraine, the subject will complete a short questionnaire (migraine symptom questionnaire) rating headache pain on a 4-point scale (0 = no pain, 1 = mild pain, 2 = moderate pain, 3 = severe pain) and associated symptoms (nausea, photophobia and phonophobia) on a binary scale, as well report if their headache is unilateral, throbbing, and aggravated by physical activity. Only subjects with Grade 2 or Grade 3 pain at baseline may be randomized to receive study intervention.

A member of the study team will obtain the subject's height, weight, tympanic membrane temperature, blood pressure, and oxygen saturation and record findings in the Case Report Form.

The study team member will ask the patient to confirm that they are of general good health, other than their migraine diagnosis, and if there are any updates to the subject's medical history and record any concomitant medications.

If the subject meets the criteria for a qualifying migraine (Grade 2 or 3 severity, onset of head pain was less than 6 hours ago), the study team member will randomize the subject.

Upon setting up the device for a subject, the study team member who will administer the therapy will run a quick test to confirm the nebulizer is propelling mist into the CoolStat airstream. Once completing the device apparatus setup, they will turn the CoolStat on and hold a piece of paper up to the airstream for 5 seconds. If the paper becomes wet, then they can move forward with treatment. If it does not become wet, they should check the attachment interface of the nebulizer and nasal mask.

---

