## 1.2 SCHEMA

### 1.3 SCHEDULE OF ACTIVITIES (SOA)

Procedure	Screening (Day -60 to 0)	Treatment Visit (Day 0)	Post Treatment (2 hours) ± 15 minutes	Post Treatment (24 hours) ± 2 hours
Informed consent	X			
Demographics	X			
Medical history	X			
Eligibility criteria verification	X			
Randomization		X		
Physical exam (height and weight)		X		
Vital signs (blood pressure, pulse oximetry, tympanic temperature)		X*	X	
Administer study intervention		X		
Most Bothersome Symptom		X		
Head pain severity score		X	X	X
Nausea severity score		X	X	X
Photosensitivity severity score		X	X	X
Phonosensitivity severity score		X	X	X
Concomitant medications review	X	X	X	X
Adverse event review and evaluation		X	X	X
Complete Case Report Forms (CRFs)	X	X	X	X

*\*Vitals will be taken immediately pre and post treatment session.*

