### 8.1.3 POST TREATMENT EVALUATION 1 (0 MINUTES)

Immediately after the CoolStat treatment is completed or discontinued, the subject will repeat the migraine symptom questionnaire and answer questions about their experience using the CoolStat.

The investigator or his designee will obtain the subject's tympanic membrane temperature, blood pressure, and oxygen saturation and record the data in the Case Report Form.

The investigator or his designee will monitor the subject for any adverse events.

---

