### 8.1.4 POST TREATMENT EVALUATION 2 (2 HOURS)

The subject will remain in the clinic for 2 hours after they complete treatment session and will be monitored for adverse events during that time period. During this 2 hour period, subjects will remain in the exam room or another quiet space in the clinic, and will be allowed to rest. Subjects will be asked to delay taking rescue medications until this 2 hour period is over, if possible.

At the end of the 2 hour monitoring period, subjects will repeat the migraine symptom questionnaire, and the investigator or his designee will obtain the subject's tympanic membrane temperature, blood pressure, and oxygen saturation and record the data in the Case Report Form.

The investigator or his designee will record any adverse events.

Upon completion of these items, the subject may resume other care activities.

The study team member will record use of any rescue medications during this 2-hour period.

---

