### 8.1.5 POST TREATMENT EVALUATION 3 (24 HOURS)

The investigator or his designee will call the subject approximately twenty-four hours after CoolStat treatment was completed and ask the subject to complete the migraine questionnaire over the phone. If the subject cannot be reached, study personnel will continue to try to reach the subject on regular intervals over the course of this day and the next consecutive 2 days. It will be noted in the case report forms if the subject could not be reached for the final follow up.

The investigator or his designee will record any additional treatments used by the subject within the 24 hours since CoolStat (e.g. NSAIDs, ice), and will also ask if they have experienced any adverse events.

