#### 9.4.2 ANALYSIS OF THE PRIMARY EFFICACY ENDPOINT(S)

Both primary efficacy endpoints are scored categorically (Grade 0: no pain, Grade 1: mild pain, Grade 2: moderate pain, Grade 3 severe pain).

These categorical data will be summarized by absolute (n) and relative (%) frequency tables.

For categorical variables/proportions, we will perform Kruskal-Wallis test (the nonparametric equivalent of the ANOVA) to determine if there is a difference across the three study groups.

If there is a difference, then the Mann-Whitney test will be performed to compare the groups to each other to determine where the difference lies. We will correct for multiple comparisons using Bonferroni correction. The multiple imputation method will be used as the primary method for handling missing data in this study.

---

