#### 9.4.3 ANALYSIS OF THE SECONDARY ENDPOINT(S)

Our secondary outcomes (pain relief and relief from symptoms at 2 hours, 24 hours and immediately after treatment) are graded on the same scale, and the same statistical methods used as for the primary outcomes will be used.

All relevant general, safety and efficacy data will be descriptively summarized at each time point.

Continuous data will be summarized by the number of patients (n), the arithmetic mean and the standard deviation, the coefficient of variation as a percentage (CV%), the median, the interquartile range, the minimum and the maximum value.

---

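### Section 8.1.2 collects the associated symptoms as yes/no, but 9.4.3 analyses symptom relief on the 0–3 pain grades; if 8.1.2 is followed, partial symptom relief cannot be recorded

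*Combined protocol and SAP*

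**What the plan says.** Section 8.1.2 describes one migraine symptom questionnaire, completed on arrival. In a single sentence it puts headache pain on a 0–3 scale and "associated symptoms (nausea, photophobia and phonophobia) on a binary scale".

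The later visits use the same instrument. In 8.1.3, right after treatment, "the subject will repeat the migraine symptom questionnaire"; in 8.1.4, at 2 hours, "subjects will repeat the migraine symptom questionnaire"; and in 8.1.5, at 24 hours, staff "ask the subject to complete the migraine questionnaire over the phone".

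Two other places treat the symptoms as graded:

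- Section 1.3, the Schedule of Activities, has rows such as "Nausea severity score" and "Photosensitivity severity score", in the same form as the head pain row. It names no scale.
- Section 9.4.3 states: "Our secondary outcomes (pain relief and relief from symptoms at 2 hours, 24 hours and immediately after treatment) are graded on the same scale". The scale meant is that of the primary outcome, given in 9.4.2 as "Grade 0: no pain, Grade 1: mild pain, Grade 2: moderate pain, Grade 3 severe pain".

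The secondary efficacy objective (sections 1.1 and 3) is that pain and the other symptoms become less severe after treatment than at baseline. Relief of symptoms and freedom from symptoms are listed as separate secondary endpoints and have separate hypotheses in 9.1. No section defines symptom relief or says how a yes/no answer becomes a grade.

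**The concern.** A symptom item cannot have both two levels and four. Because 8.1.2 contrasts the two scales within one sentence, a loose choice of words is less likely, and sites work from that section. If the form follows it, the database will show whether a symptom was present but not how bad it was. That cannot be repaired at analysis, because a grade that was never asked for cannot be reconstructed. At stake are the symptom half of the severity objective and the meaning of symptom relief as an endpoint distinct from symptom freedom. The study also aims to supply effect sizes for a pivotal trial, so a lost symptom grade would be missed there too.

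**Working it through.** **The plan's own figure.** The plan gives no calculated figure for symptoms. Its one calculation is the 17 per group in 9.2, from 56% versus 8%, two-sided alpha 0.05 and 80% power. Fisher's exact test has power 77.4% at 16 per group and 81.3% at 17, so the 17 is reproduced. Its input is freedom from headache pain at 2 hours, so nothing below changes it.

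**Step 1: can the sections agree?** Collection (8.1.2, reused in 8.1.3 to 8.1.5) gives two levels per symptom. Analysis (9.4.3 with 9.4.2) needs four. With no mapping stated, the two are incompatible. The severity-score rows in 1.3 lean towards grades but do not settle the scale.

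**Step 2: what does yes/no hide?** Take a subject with the symptom at baseline grade b (1, 2 or 3). An improvement is any follow-up grade f below b.

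- b = 1: 1 to 0 (one change)
- b = 2: 2 to 0, 2 to 1 (two changes)
- b = 3: 3 to 0, 3 to 1, 3 to 2 (three changes)

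That makes 1 + 2 + 3 = 6 improving changes. Yes/no shows only those ending at 0, of which there are 3. The hidden ones are 6 − 3 = 3: 2 to 1, 3 to 1 and 3 to 2. This counts kinds of change, not patients; the documents do not say how often each would occur.

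**Step 3: relief versus freedom.** For one symptom present at baseline, the only improvement visible on yes/no is from yes to no. That is also freedom from the symptom, so the two endpoints are the same event. If the three symptoms are combined they can still differ: a subject who goes from three symptoms to one has improved but is not symptom-free.

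**Step 4: what still works?** The rank tests of 9.4.2 run on 0/1 data. For N subjects the Kruskal-Wallis statistic is then H = χ² × (N − 1)/N, where χ² is Pearson's statistic for the table of proportions. In an invented example with three arms of 25, of whom 14, 10 and 5 are symptom-free, χ² = 6.859 and H = 6.859 × 74/75 = 6.768. The test therefore compares proportions with the symptom, not grades. Freedom can be analysed in full from yes/no answers. The relief hypotheses in 9.1 are also about proportions, so they can be tested once relief has been defined.

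**Step 5: how much data?** Three symptoms × 4 time points (baseline, 0 minutes, 2 hours, 24 hours) × 75 randomized subjects = 900 ratings. This is a ceiling, because 5.4 allows up to 75 subjects. Under 8.1.2 none of these ratings carries a grade.

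**The case against.** The best reply is that little breaks. The tests named in 9.4.2 accept yes/no data, the 9.1 hypotheses are about proportions, and only secondary endpoints are touched. All of that stands. A reader might infer that 9.4.3 as a whole cannot be carried out. The documents do not support that: its pain outcomes are graded 0–3 throughout, and its methods remain computable for the symptoms.

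The second reply is that the real form may be graded, which would make 8.1.2 a wording error with no data lost. That is possible, since the questionnaire is not in the documents. The contradiction is certain; the loss is conditional on the form. Even so, 8.1.2 would need correcting.

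The third reply is that the Schedule of Activities may be using severity score as a row label only. That is fair, and the firm conflict is between 8.1.2 and 9.4.3.

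A reader might also infer a serious loss of power. The documents give no symptom grade distribution, prevalence or response rate, so any power figure would rest on assumed inputs. None is claimed here.

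**Conclusion.** The inconsistency is present in the current text and should be corrected. If 8.1.2 is followed, none of up to 900 symptom ratings can be graded 0–3, three of the six kinds of improvement go unrecorded, the symptom part of the severity objective is not measured, and relief of a single symptom present at baseline cannot be told apart from freedom. This rests on two assumptions: that the form matches 8.1.2, and that the 24-hour phone questionnaire is the same instrument. The harm is confined to the symptom-severity objective and the symptom relief endpoint. Pain outcomes, symptom freedom, the primary endpoints and the sample size stand. It would go too far to infer that relief and freedom are always identical under yes/no, because a combined symptom outcome can separate them.

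**What to change.** Amend 8.1.2 so that nausea, photophobia and phonophobia are each rated 0–3 (none, mild, moderate, severe) at baseline, 0 minutes, 2 hours and 24 hours. This fits the Schedule of Activities, 9.4.3 and the stated objective. In 9.4.3, define symptom relief as a prespecified drop in grade from baseline, and freedom as grade 0. Check the questionnaire and case report form against the amended text. The documents do not give the study's status; any answers already taken as yes/no could not be upgraded later.

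If the sponsor prefers yes/no, align the Schedule of Activities and 9.4.3 with it, redefine symptom relief in terms that yes/no data can show (for example, fewer symptoms than at baseline), and reword the severity objective for symptoms.

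The cost is four response options instead of two on three existing items, plus a few defining sentences. No visit or procedure is added.

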### 8.1.3 POST TREATMENT EVALUATION 1 (0 MINUTES)

Immediately after the CoolStat treatment is completed or discontinued, the subject will repeat the migraine symptom questionnaire and answer questions about their experience using the CoolStat.

The investigator or his designee will obtain the subject's tympanic membrane temperature, blood pressure, and oxygen saturation and record the data in the Case Report Form.

The investigator or his designee will monitor the subject for any adverse events.

---

### 8.1.4 POST TREATMENT EVALUATION 2 (2 HOURS)

The subject will remain in the clinic for 2 hours after they complete treatment session and will be monitored for adverse events during that time period. During this 2 hour period, subjects will remain in the exam room or another quiet space in the clinic, and will be allowed to rest. Subjects will be asked to delay taking rescue medications until this 2 hour period is over, if possible.

At the end of the 2 hour monitoring period, subjects will repeat the migraine symptom questionnaire, and the investigator or his designee will obtain the subject's tympanic membrane temperature, blood pressure, and oxygen saturation and record the data in the Case Report Form.

The investigator or his designee will record any adverse events.

Upon completion of these items, the subject may resume other care activities.

The study team member will record use of any rescue medications during this 2-hour period.

---

### 8.1.5 POST TREATMENT EVALUATION 3 (24 HOURS)

The investigator or his designee will call the subject approximately twenty-four hours after CoolStat treatment was completed and ask the subject to complete the migraine questionnaire over the phone. If the subject cannot be reached, study personnel will continue to try to reach the subject on regular intervals over the course of this day and the next consecutive 2 days. It will be noted in the case report forms if the subject could not be reached for the final follow up.

The investigator or his designee will record any additional treatments used by the subject within the 24 hours since CoolStat (e.g. NSAIDs, ice), and will also ask if they have experienced any adverse events.

## 8.2 SAFETY AND OTHER ASSESSMENTS

- **Physical examination** including height, weight and temperature will be obtained at baseline
- **Vital signs** will be taken at baseline, immediately post treatment session, and at 2 hours post treatment
- **Administration of questionnaires** immediately post treatment, at 2 hours and 24 hours post treatment.
- **Assessment of adverse events.** Patients with ongoing AEs/SAEs will be followed up with on a daily basis until the AE/SAEs are deemed to be resolved.

## 8.3 ADVERSE EVENTS AND SERIOUS ADVERSE EVENTS

---

### 8.3.1 DEFINITION OF ADVERSE EVENTS (AE)

Adverse event means any untoward medical occurrence associated with the use of an intervention in humans, whether or not considered intervention-related (21 CFR 312.32 (a)).

---

### 8.3.2 DEFINITION OF SERIOUS ADVERSE EVENTS (SAE)

An adverse event (AE) or suspected adverse reaction is considered "serious" if, in the view of either the investigator or sponsor, it results in any of the following outcomes: death, a life-threatening adverse event, inpatient hospitalization or prolongation of existing hospitalization, a persistent or significant incapacity or substantial disruption of the ability to conduct normal life functions, or a congenital anomaly/birth defect.

Important medical events that may not result in death, be life-threatening, or require hospitalization may be considered serious when, based upon appropriate medical judgment, they may jeopardize the participant and may require medical or surgical intervention to prevent one of the outcomes listed in this definition.

---

### 8.3.3 CLASSIFICATION OF AN ADVERSE EVENT

---

#### 8.3.3.1 SEVERITY OF EVENT

For adverse events (AEs), the following guidelines will be used to describe severity.

- **Mild** – Events require minimal or no treatment and do not interfere with the participant’s daily activities.
- **Moderate** – Events result in a low level of inconvenience or concern with the therapeutic measures. Moderate events may cause some interference with functioning.
- **Severe** – Events interrupt a participant’s usual daily activity and may require systemic drug therapy or other treatment. Severe events are usually potentially life-threatening or incapacitating. Of note, the term “severe” does not necessarily equate to “serious”.

---

#### 8.3.3.2 RELATIONSHIP TO STUDY INTERVENTION

All adverse events (AEs) must have their relationship to study intervention assessed by the clinician who examines and evaluates the participant based on temporal relationship and his/her clinical judgment. The degree of certainty about causality will be graded using the categories below. In a clinical trial, the study product must always be suspect.

- **Related** – The AE is known to occur with the study intervention, there is a reasonable possibility that the study intervention caused the AE, or there is a temporal relationship between the study intervention and event. Reasonable possibility means that there is evidence to suggest a causal relationship between the study intervention and the AE.
- **Not Related** – There is not a reasonable possibility that the administration of the study intervention caused the event, there is no temporal relationship between the study intervention and event onset, or an alternate etiology has been established.

---

#### 8.3.3.3 EXPECTEDNESS

The Principal Investigator will be responsible for determining whether an adverse event (AE) is expected or unexpected. An AE will be considered unexpected if the nature, severity, or frequency of the event is not consistent with the risk information previously described for the study intervention.

---

### 8.3.4 TIME PERIOD AND FREQUENCY FOR EVENT ASSESSMENT AND FOLLOW-UP

The occurrence of an adverse event (AE) or serious adverse event (SAE) may come to the attention of study personnel during study visits and interviews of a study participant presenting for medical care, or upon review by a study monitor.

All AEs including local and systemic reactions not meeting the criteria for SAEs will be captured on the appropriate case report form (CRF). Information to be collected includes event description, time of onset, clinician's assessment of severity, relationship to study product (assessed only by those with the training and authority to make a diagnosis), and time of resolution/stabilization of the event. All AEs occurring while on study must be documented appropriately regardless of relationship. All AEs will be followed to adequate resolution.

Any medical condition that is present at the time that the participant is screened will be considered as baseline and not reported as an AE. However, if the study participant's condition deteriorates at any time during the study, it will be recorded as an AE.

Changes in the severity of an AE will be documented to allow an assessment of the duration of the event at each level of severity to be performed. AEs characterized as intermittent require documentation of onset and duration of each episode.

The study coordinator(s) will record all reportable events with start dates occurring any time after informed consent is obtained until 1 (for non-serious AEs) or 7 days (for SAEs) after the last day of study participation. At each study visit, the investigator will inquire about the occurrence of AE/SAEs since the last visit. Events will be followed for outcome information until resolution or stabilization.

---

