**Endpoints:**

Primary Endpoints:

- Safety of the CoolStat device measured by incidence of adverse events
- Tolerability of the CoolStat device by percent of subjects who fail to complete the full treatment session.
- Pain relief at 2 hours post treatment.

Secondary Endpoints:

- Pain relief immediately post treatment and at 24 hours post treatment.
- Pain freedom immediately, 2 hours, and 24 hours post treatment.
- Relief of migraine associated symptoms (nausea/vomiting, photophobia, phonophobia) immediately, 2 hours, and 24 hours post treatment.
- Freedom from migraine associated symptoms (nausea/vomiting, photophobia, phonophobia) immediately, 2 hours, and 24 hours post treatment.
- Use of rescue medication between 2 and 24 hours.
- % of subjects who believe they received active treatment in each arm.

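### Worsening of the treated migraine counts in the primary AE incidence, because Section 8.3.4 sets baseline at screening and has no rule for the attack under treatment

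*Combined protocol and SAP*

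**What the plan says.** The first primary endpoint in the Synopsis, repeated in Section 3, is "Safety of the CoolStat device measured by incidence of adverse events". It is not limited to device-related events, and Section 8.3.4 is explicit about recording: "All AEs occurring while on study must be documented appropriately regardless of relationship".

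The baseline for AEs is set in the same section: "Any medical condition that is present at the time that the participant is screened will be considered as baseline and not reported as an AE". The next sentence reads: "However, if the study participant's condition deteriorates at any time during the study, it will be recorded as an AE". The Schedule of Activities places screening anywhere from Day -60 to Day 0. Sections 5.4 and 8.1.1 let subjects be screened first and come back later during an attack.

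Head pain, nausea, photophobia and phonophobia are collected on the migraine questionnaire before treatment, immediately after it, at 2 hours and at 24 hours (Sections 8.1.2 to 8.1.5). AEs are sought at the same post-treatment contacts.

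Section 8.3.3.2 has relatedness "assessed by the clinician who examines and evaluates the participant based on temporal relationship and his/her clinical judgment". The last of three alternative routes to *Related* is "or there is a temporal relationship between the study intervention and event". *Not Related* also has alternative routes, the last two being "there is no temporal relationship between the study intervention and event onset, or an alternate etiology has been established".

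Section 8.3.5 requires each AE to be listed individually with description and relationship. Section 9.4.4 tabulates safety data by arm without hypothesis tests and does not mention tabulation by event term.

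**The concern.** Nothing in the protocol separates the course of the treated attack from adverse events. A disease-related event category appears only in the abbreviation list. A move from Grade 2 to Grade 3 pain, nausea that first appears at 2 hours, or return of the attack by 24 hours is a deterioration under Section 8.3.4. It is also an efficacy observation. For a subject screened between attacks, the symptoms of the treated attack were not present at the AE baseline at all.

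The primary safety endpoint therefore mixes device effects with the course of the disease. If worsening is equally common in all arms, the between-arm difference shrinks. If the device works and worsening is more common on sham, the disease component runs against any excess of nasal irritation in the active arms. Sites (up to three) may also differ in what they enter, and with 25 subjects per arm each subject moves an arm's incidence by 1/25 = 4 points.

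The overlap in Section 8.3.3.2 is a second, separate defect. Worsening after treatment meets *Related* by timing and can meet *Not Related* by alternate etiology, and the section does not say which prevails.

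**Working it through.** **The plan's own figure.** The documents state no AE or worsening rate, so there is no safety figure to reproduce. The only design figure is the efficacy sample size in Section 9.2: at least 17 per group for 56% against 8%, 80% power, two-sided 0.05. Exact power of Fisher's test is 77.4% at 16 and 81.3% at 17 per group, so it reproduces. Here it matters only because it led to the 25 per arm.

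**Does treated-migraine worsening count as an AE?** There are two readings of Section 8.3.4:
- Migraine, diagnosed for at least a year at entry, is a baseline condition. Its deterioration is then an AE.
- The attack began after screening. Its symptoms are then not baseline.

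Neither reading exempts worsening. Section 7.1 points the same way, since any new clinically relevant finding is to be reported as an AE. The one exception in Section 8.3.5 concerns clinically insignificant physical findings, not symptoms. The rule has limits: persistence without relief is not deterioration, and Grade 3 pain cannot worsen on a 0 to 3 scale.

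**Size, with assumed rates.** Let d be the proportion of an arm with a device-caused AE and b the proportion with treated-migraine worsening, taken as independent. Recorded incidence is 1 − (1 − d)(1 − b). Assume d = 20% on one active arm and 5% on sham, a 15-point excess.

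| Worsening, active / sham | Active | Sham | Excess |
|---|---|---|---|
| 0% / 0% | 20% | 5% | 15 points |
| 5% / 5% | 1 − 0.80 × 0.95 = 24% | 1 − 0.95 × 0.95 = 9.75% | 14.25 points |
| 15% / 15% | 1 − 0.80 × 0.85 = 32% | 1 − 0.95 × 0.85 = 19.25% | 12.75 points |
| 5% / 15% | 1 − 0.80 × 0.95 = 24% | 1 − 0.95 × 0.85 = 19.25% | 4.75 points |

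With equal worsening the excess is simply 15 × (1 − b) points. The last row would arise, for example, if half of each arm started at Grade 2 and 10% (active) or 30% (sham) of those moved to Grade 3.

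**Sensitivity to the device rates.** With d = 30% active and 4% sham (26 points), equal worsening of 10%, 30% and 50% leaves 23.4, 18.2 and 13 points. Worsening of 10% active against 40% sham gives 37% against 42.4%, so the sign reverses. That needs a fourfold difference in worsening.

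**Relatedness.** Take new nausea at 2 hours. It follows treatment, so the timing route to *Related* is met. If the clinician puts it down to the migraine, the alternate-etiology route to *Not Related* is met as well. Both labels fit and no order of precedence is given.

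**The case against.** Broad AE capture is defensible in an early device study, and Section 8.3.3.2 itself says the product should always be suspected. That stands, and is why worsening should go on being recorded. The examples of AEs from the earlier CoolStat study (Section 2.2) are nasal, so sites may in practice leave migraine symptoms off the AE form. That would be unwritten practice, and it is not what Section 8.3.4 says.

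Section 8.3.5 starts AE reporting at treatment or randomization, so symptoms already present at the pre-treatment questionnaire fall outside its window. Section 8.3.4, however, has coordinators "record all reportable events with start dates occurring any time after informed consent is obtained". The two windows need reconciling, and neither excludes worsening after treatment.

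Several stronger readings are tempting and are not supported:
- *Migraine events enter the primary endpoint as device-related.* The endpoint counts all AEs, so relatedness does not decide entry.
- *Every event after treatment must be called Related.* Clinical judgment and the alternate-etiology route leave room for *Not Related*, and Section 8.3.5 expects temporally associated AEs that are not considered related. It does not follow that related AEs would equal all AEs, and Section 9.4.4 specifies no related-AE table.
- *The overlap would drive unblinding.* Section 6.3 permits, and does not require, unblinding for an SAE judged related. A one-grade pain increase or new nausea is not in itself an SAE under Section 8.3.2.
- *Device harm would be hidden.* The anticipated device effects in Section 2.3.1 are nasal, sinus and mouth complaints, distinct from migraine symptoms. The listings show them individually, and failure to complete the session is its own primary endpoint.

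**Conclusion.** The point holds in limited form. Under Section 8.3.4 as written, worsening, new symptoms or recurrence of the treated attack count in the primary all-AE incidence as well as in efficacy. This can dilute the between-arm difference, or offset it if worsening is more frequent on sham. The size is unknown. On the main illustration a 15-point excess falls to between 14.25 and 12.75 points with equal worsening of 5% to 15%, and to 4.75 points only when sham worsening is taken as three times active. Every rate is an assumption, as is independence of the two kinds of event. The effect is confined to aggregate incidence. The overlap of *Related* and *Not Related* is real, but touches only the relationship classification. Both are worth correcting because the changes are cheap and make a primary endpoint interpretable.

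**What to change.** 1. In Section 8.3.4, take the pre-treatment questionnaire on the treatment day as the baseline for migraine symptoms, and state whether return of pain after relief counts as deterioration.
2. Keep recording worsening of the treated migraine, but report AE incidence by arm both with and without treated-migraine events. Add a by-arm table of worsening from the questionnaire, so that worsening caused by the device stays visible.
3. In Section 8.3.3.2, make the categories mutually exclusive. Remove timing alone as sufficient for *Related*, and keep a known association or a reasonable possibility as alternative routes. Allow *Not Related* only when there is no reasonable possibility that the device caused the event.

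Two tempting shortcuts should be avoided. Joining the three routes to *Related* with *and* would require every related event to be already known, so a new device effect could never qualify. Letting the migraine diagnosis alone decide *Not Related* would dismiss device-provoked head pain, since every subject has migraine.

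The cost is protocol wording, brief site training and one or two extra tables from data already collected. The downside is a site judgement on which events belong to the treated migraine; showing incidence both ways limits its influence.
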